## 5. Analysis Sets

Efficacy analysis will be performed in the largest analysis set (hereinafter, FAS). Safety analysis will be performed in the safety analysis set.

The analysis sets are defined below; however, details of the treatment of subjects should be determined by the sponsor by the time the data are fixed.

## 5.1 Efficacy analysis set

The analysis set consisting of all subjects transitioned to the treatment period excluding the following subjects is the FAS.

- ✓ Subjects who did not have anemia associated with PD-CKD
- ✓ Subjects who have never received a dose of the study drug
- ✓ Subjects with no efficacy data after the first day of study drug administration

## 5.2 Safety analysis set

The analysis set consisting of all subjects transitioned to the treatment period excluding the following subjects is the safety analysis set.

- ✓ Subjects who have never received a dose of study drug
- ✓ Subjects with no safety data after the first of study drug administration

## 6. Patient Cohorts

The patient cohorts are defined below. Each patient cohort should be analyzed as needed.

Correction cohort: A group of patients who have not received ESA formulations from 8 weeks prior to the first day of the screening period.

Conversion cohort: A group of patients who have received ESA formulations from 8 weeks prior to the first day of the screening period.

Conversion (Hb value  $\geq 11.0$ ) cohort: A subset of patients in the Conversion cohort whose mean Hb value during the last 2 screening sessions is  $\geq 11.0$  g/dL.

Conversion (Hb value  $< 11.0$ ) cohort: A subset of patients in the Conversion cohort whose mean Hb value during the last 2 screening sessions is  $< 11.0$  g/dL.

As the number of patients in the Correction cohort is small, only the individual time course diagram of Hb values will be prepared.

## 7. Data Handling

Data should be handled as follows:

### 7.1 Handling of missing data

If test measurements are missing or if problems with samples etc. result in invalid measurements or reference values, these should be handled as missing values. Derived variables should also be treated as missing if even one test value or other data required for derivation is missing or not adopted.

## **7.2 Handling of data for tabulation at each evaluation time point**

Data that meet the permitted range specified in the “Table 9.1-1 Permitted range of study visits” section of the protocol should be used for the tabulation at each evaluation time point and should not be imputed with those outside the permitted range.

If there are multiple data within the permitted range, then the one closer to the reference date should be adopted. If the deviations from the reference date are the same, data for the efficacy and safety evaluations should be adopted before and after the reference date, respectively.

## **7.3 Handling of efficacy endpoints if rescue therapy is performed**

If rescue therapy is performed, data from the day after rescue therapy should not be used for efficacy analysis.

## **7.4 Imputation of missing data**

The mixed model repeated measures (MMRM) used to analyze the efficacy endpoint should not use data imputing missing data. If there are missing data at the first day of the treatment period, data from the day closest to the first day of the treatment period should be used as data for the first day of the treatment period.

For the primary endpoint, the mean Hb values at Weeks 20 and 24 of the treatment period, missing data are imputed with data from the evaluation period immediately before the missing evaluation period (excluding the first day of the treatment period) (LOCF method). When any one evaluation time points has missing data, the data at the evaluation time point closest to the missing evaluation time point is adopted, and when two evaluation time points have missing data, the data in the two different evaluation time points closest to and before the missing evaluation time points should be adopted to calculate the mean Hb value. However, Hb values at the same evaluation time point should not be used.

In addition, data imputed by the LOCF method at Week 24 of the treatment period should also be derived for clinical laboratory value, vital sign, QOL indices for the efficacy analysis. Imputed with missing date of Week 24 of the treatment period will be used as data of the completion of treatment period.

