## 9. Tests and observations

### 9.1 Test and observation schedule

Item	VISIT	Screening period [a]		Treatment period											Final day of follow-up observation period [b]
		Informed consent	First day	Visit 2	First day [c]	W2	W4	W6	W8	W10	W12	W16	W20	W24	
Visit no.	IC	SV1	SV2	TV1	TV2	TV3	TV4	TV5	TV6	TV7	TV8	TV9	TV10	TV11	FU
Permitted range (day)	-	-	-	-	±3	±3	±3	±3	±3	±3	±7	±7	±7	+ 7 or + 14 [d]	+7
Procedure/evaluation															
Informed consent	X														
Inclusion/exclusion criteria	X	X	X	X											
Patient's background and history	X			X											
Height				X											
Body weight (weight excluding dialysis solution)				X						X			X	X	
Folic acid and vitamin B 12		X													
Pregnancy test [e]		X											X	X	
Haematology test		X	X [f]	X	X	X	X	X	X	X	X	X	X	X	X
Blood biochemistry test		X		X	X	X	X	X	X	X	X	X	X	X	X
C-reactive protein		X		X									X	X	
Iron-related measures		X		X	X	X	X	X	X	X	X	X	X	X	X
Hepcidin				X	X	X	X			X			X	X	
Erythropoietin				X	X	X	X			X			X	X	
VEGF				X						X			X	X	
Urinalysis (qualitative)		X		X	X	X	X	X	X	X	X	X	X	X	X
Vital signs [g]		X		X	X	X	X	X	X	X	X	X	X	X	X
12-lead ECG [h]				X									X	X	
Fundoscopy [d]			X										X	X	
Chest X-ray [d]			X										X	X	
QOL measures (EQ-5D-5L, KDQOL)				X						X			X	X	
AE investigations				X	X	X	X	X	X	X	X	X	X	X	X
Blood sampling for genetic analysis [i]					Blood sampling should be performed once as early as possible after 2 weeks of										
Drug evaluation/procedure															
Investigation of concomitant drugs				X	X	X	X	X	X	X	X	X	X	X	X
Prescribing MT-6548 tablets [j]				Administration according to the dosage adjustment guideline											
Administration of iron supplements				Administer iron supplements to maintain serum ferritin values ≥100 ng/mL or TSAT ≥20%.											

[a] Maximum screening period length is 6 weeks. Test results will be reviewed prior to transitioning from the first day of the screening period to screening period Visit 2, and from screening period Visit 2 to the first day of the treatment period. Re-testing will be performed as necessary.

[b] Not required if withdrawing prior to treatment period.

[c] Perform prior to study drug treatment (AE investigations begin after study drug treatment)

[d] Fundoscopy and chest X-ray performed once during screening period. Also performed once between treatment period Weeks 20 and 24, and to extent possible within 14 days of study withdrawal.

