### 9.2.3 Efficacy endpoints

Blood sampling will be performed at each study center for measurement by the contract laboratory testing facility. All measurement results will be reported to each study center and the study sponsor.

(1) Hb value

Blood sampling and Hb measurement will be performed on the first day of the screening period, screening period Visit 2, the first day of the treatment period, Weeks 2, 4, 6, 8, 10, 12, 16, 20, and 24 of the treatment period, and the day of discontinuation of treatment.

(2) Ratio of subjects who received ESA rescue therapy

If ESA rescue therapy is performed, type of ESA formulation used, administration route, dose interval, and dosage will be recorded in the CRF.

(3) Ratio of subjects who received red blood cell (RBC) transfusion rescue therapy.

If RBC transfusion rescue therapy is performed, type of RBC formulation used and dosage will be recorded in the CRF.

(4) Study drug dosage

Study drug dosage will be recorded in CRFs.

(5) total number of dosage adjustments

Yes/no for MT-6548 dosage adjustments and post-adjustment dosage will be recorded in the CRF.

(6) Quantity of iron administered

Iron dosage will be recorded in CRFs.

(7) Ratio of subjects who received IV iron

Iron administration route will be recorded in CRFs.

(8) Iron-related measures (serum iron, TIBC, TSAT, and serum ferritin)

Blood sampling and measurement will be performed for serum iron, TIBC, TSAT, and serum ferritin on the first day of the screening period, the first day of the treatment period, Weeks 2, 4, 6, 8, 10, 12, 16, 20, and 24 of the treatment period, and the day of discontinuation of treatment.

(9) Hepcidin

Blood sampling and measurement of hepcidin will be performed on the first day of the treatment period, treatment period Weeks 2, 4, 6, 12, and 24, and the day of discontinuation of treatment.

(10) Haematocrit, RBC count

Blood sampling and measurement will be performed for haematocrit and RBC count on the first day of the screening period, the first day of the treatment period, Weeks 2, 4, 6, 8, 10, 12, 16, 20, and 24 of the treatment period, and the day of discontinuation of treatment.

(11) Reticulocytes (counts and fractions)

Blood sampling and measurement will be performed for reticulocytes (counts and fractions) on the first day of the screening period, the first day of the treatment period, Weeks 2, 4, 6, 8, 10, 12, 16, 20, and 24 of the treatment period, and the day of discontinuation of treatment.

(12) EPO

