Blood sampling and measurement of EPO will be performed on the first day of the treatment period, treatment period Weeks 2, 4, 6, 12, and 24, and the day of discontinuation of treatment. Blood sampling time will be recorded in CRFs.

(13) QOL measures (EQ-5D-5L, KDQOL)

Subjects will fill out EQ-5D-5L and KDQOL questionnaires (Appendices 4 and 5) on the first day of the treatment period, treatment period Weeks 12 and 24, and the day of discontinuation of treatment, and results recorded in CRFs.

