#### (2) Handling of timepoint data for statistical summaries at each measurement timepoint

Statistical summaries for each evaluation timepoint will use data compliant with permitted ranges as described in “Table 9.1-1 Permitted ranges for study center visits.” There will be no supplementing with data from outside the permitted range.

If multiple data points exist within the permitted range, then the one closest to the scheduled day will be used. If there are deviations from the scheduled day, then data points prior to the scheduled day will be used for efficacy evaluation, and data points after the scheduled day will be used for safety evaluation.

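### SAP 7.4 lets an on-treatment value replace a missing first-day baseline, so for hepcidin, EPO, QOL and body weight the scheduled substitute is always post-dose

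*SAP*

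**What the plan says.** SAP 7.4 deals with a missing value on the first day of the treatment period (Day 0 in protocol Table 9.1-1) in one sentence: "data from the day closest to the first day of the treatment period should be used" in its place. It gives no direction, no time window and no pre-dose condition. The sentence before it says that the MMRM "should not use data imputing missing data". The errata leave 7.4 unchanged.

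Three other parts of the plan bear on this:

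- **Timing of the scheduled tests.** Footnote [c] to the protocol 9.1 schedule requires the first-day tests to be done before dosing.
- **Visit windows.** SAP 7.2 says that data for a time point "should not be imputed with those outside the permitted range". Protocol 13.2(2) agrees: "There will be no supplementing with data from outside the permitted range". Table 9.1-1 gives Day 0 no permitted range.
- **Measurement schedule (protocol 9.2.3 and 9.2.4.1).** "Blood sampling and measurement of hepcidin will be performed on the first day of the treatment period", and the next sample is at Week 2; EPO follows the same schedule. "Subjects will fill out EQ-5D-5L and KDQOL questionnaires" on the first day and then at Weeks 12 and 24. Body weight is also taken on the first day and at Weeks 12 and 24. All of these are repeated at discontinuation, and none is scheduled at screening. Hb is measured at both screening visits. Iron measures are taken at the first screening visit only, because the second visit measures Hb alone.

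**The concern.** A baseline should describe the subject before treatment. Under 7.4 as written, a value obtained on MT-6548 can become the reference for change. If it comes from a scheduled visit, the same number is both baseline and result at that visit.

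These changes feed the paired t-tests and change-from-baseline MMRMs of SAP 8.5.1(2) and 8.5.2, and the body weight summaries of 8.6.4. The study has no control group, so change from the first day is the main within-subject contrast for these variables.

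A missing first-day value needs nothing unusual. SAP 7.1 turns an invalid sample into a missing value, and SAP 4.15 makes the EQ-5D-5L index missing if one of its five items is blank.

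**Working it through.** **The plan's own figure.** The only design figure is the precision of mean Hb in SAP 2.3 (n = 40, SD = 1.78, two-sided 95%). The half-width is t(0.975, 39) × 1.78/√40 = 0.569, which rounds to the stated ±0.57 g/dL. It does not depend on the baseline rule.

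**Step 1: variables with no screening measurement.** No scheduled value precedes the first day, so the closest scheduled value is on treatment: Week 2 (Day 11–17) for hepcidin and EPO, and Week 12 (Day 81–87) for QOL and body weight. A discontinuation visit takes its place if it comes earlier. Only an unscheduled pre-dose measurement could prevent this.

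**Step 2: Hb and iron measures.** Let g be the number of days from the last screening value to Day 0. Screening may last 6 weeks, so g can reach 42. Compare g with the day of the Week 2 sample:

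| Week 2 sample on | Screening value is closer | Week 2 value is closer |
|---|---|---|
| Day 11 | g = 1 to 10 | g = 12 to 42 |
| Day 14 | g = 1 to 13 | g = 15 to 42 |
| Day 17 | g = 1 to 16 | g = 18 to 42 |

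For Hb, g runs from the second screening visit or a later re-test. For iron measures it runs from the first screening visit unless they were re-tested. For equal distances SAP 7.2 says "data for the efficacy and safety evaluations should be adopted before and after the reference date, respectively". If that rule extends to 7.4, which is not stated, an efficacy tie goes to the screening value.

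**Step 3: effect on one subject.** Let B be the true first-day value, Y_v the value at visit v, and d = Y_k − B the true change at the borrowed visit k.

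- Computed change at v = Y_v − Y_k = (Y_v − B) − d.
- At v = k this is exactly 0. At every other visit the change is shifted by −d.
- The shift has no fixed direction. For example, with Hb 11.0 on the first day, 10.5 at Week 2 and 11.0 at Week 24 (illustrative values), the true Week 24 change is 0 but the computed change is 11.0 − 10.5 = +0.5.

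A borrowed unscheduled on-treatment value also shifts the changes but does not force a zero at a scheduled visit.

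**Step 4: effect on the mean.** Suppose m of n = 40 subjects are affected and have the average change d. Then the mean change shifts by −d·m/40. At the borrowed visit the relative shrinkage is m/40: 1/40 = 2.5%, 2/40 = 5%, 4/40 = 10%. For Hb, with assumed values of d:

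| d (g/dL) | m = 1 | m = 2 | m = 4 |
|---|---|---|---|
| 0.5 | −0.0125 | −0.025 | −0.05 |
| 1.0 | −0.025 | −0.05 | −0.10 |

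With negative d the signs reverse. Neither m nor d is in the documents; n = 40 is the target sample size.

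**Step 5: the plan's other rules.** Day 0 has no permitted range, so taking a value from any other day is what SAP 7.2 and protocol 13.2(2) rule out. SAP section 9, as corrected by the errata, lists only the dropped Correction cohort analyses and not this exception.

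**The case against.** The strongest defence is that 7.4 leaves the direction open rather than allowing post-dose values. The SAP is a translation. In the same section, closest is used without a direction inside the LOCF rule, where an earlier value is meant. The scheduled first-day tests are themselves pre-dose. This has some force for Hb and iron measures, which have earlier values to choose. It does not help the variables in Step 1: they have no scheduled earlier value, and the rule still says that a value should be used.

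A second defence is that the certain part concerns endpoints other than the primary ones, in what may be very few subjects. That limits the size of the problem but does not justify the rule.

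A reader might also infer more than the documents support:

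- **That Hb baselines are generally on treatment.** Step 2 shows that this depends on the screening gap. The 6-week limit runs from the first screening visit, whereas for Hb the relevant gap starts at the second visit or a re-test.
- **That the substituted value is the MMRM covariate.** The sentence before the rule bars imputed data from the MMRM. Whether a substituted first-day value counts as imputed is not stated.
- **That estimated change always moves toward zero.** For an affected subject this is guaranteed only at the borrowed visit.
- **That the forced zeros narrow the confidence interval.** If a random fraction p of changes with mean δ and SD σ is set to 0, the variance becomes (1−p)σ² + p(1−p)δ². This exceeds σ² when |δ| > σ/√(1−p). At p = 4/40 the threshold is 1.05σ, so the interval can widen as well as narrow.

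**Conclusion.** The point holds in a limited form. SAP 7.4 has no pre-dose restriction. For hepcidin, EPO, EQ-5D-5L, KDQOL and body weight, following it literally makes an on-treatment value the baseline unless an unscheduled pre-dose measurement exists. For Hb and iron measures the effect depends on the gap between screening and the first day.

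The size is probably small: 2.5% to 10% of the mean change at the borrowed visit, if 1 to 4 of 40 subjects are affected and have average change. For an affected subject the whole change at that visit is lost, which for QOL means the full 12-week change. The observed mean Hb at Weeks 20 and 24 uses no baseline and is not affected. Its MMRM estimate could be affected only through the covariate, which 7.4 leaves unclear.

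The conflict with SAP 7.2 and protocol 13.2(2) does not depend on any of these assumptions.

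**What to change.** Replace the sentence in SAP 7.4 with:

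> If the value on the first day of the treatment period is missing, the last value measured before the first dose of MT-6548 is used as baseline, including as the MMRM covariate. If there is none, baseline is missing and the subject is excluded from change-from-baseline analyses of that variable.

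State this in 7.4 as an explicit exception to SAP 7.2, and list it in SAP section 9 as a departure from protocol 13.2(2).

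There are two costs. A few subjects without any pre-dose value drop out of the change analyses for that variable. Where a screening value exists, one up to 6 weeks old may serve as baseline. The ±0.57 g/dL precision statement does not change.

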## **7.5 Handling of clinical laboratory test values, such as those less than the limit of quantification**

If the measured values are reported to be not more than the limit of quantification, less than the limit of quantification, or impossible to calculate, the following handling procedures should be applied for tabulation, and missing values or zero values should not be used.

[Handling of quantification limit values]

- (1) If the measurement is reported as less than the limit of quantification

The value obtained by adding the following processing to the limit of quantification value is used as an alternative value for tabulation.

- 1) After checking the number of significant figures of the applicable item, 1 should be subtracted from the significant figure of the lowest reported quantification limit value.
- 2) It should then be expanded by one digit to a smaller number and 9 is set.

Example) Report: less than 3 Effective number of the measuring facility: up to ones digit

→ Tabulation handling: 2.9

Report: less than 500 Effective number of the measuring facility: up to tens digit

→ Tabulation handling: 499

- (2) When the measured value is reported as not more than the limit of quantification or not less than the upper limit of quantification, the limit of quantitation itself should be used as a substitute value for tabulation.

Example) Not more than the limit of quantification

Report:  $\leq 10$  → Tabulation handling: 10

Not less than the limit of quantification

Report:  $\geq 20$  → Tabulation handling: 20

## 8. Statistical Method

### 8.1 Basic matters

#### 8.1.1 Level of significance and confidence coefficient

When implementing tests, level of significance should be set at 2-sided 5%. Confidence interval (CI) will be 2-sided with a confidence coefficient of 95%.

#### 8.1.2 Descriptive statistics to calculate

Types of continuous variables to be calculated for each descriptive statistics item are provided below. Number of subjects, mean, standard deviation (SD), median, minimum, maximum, and 2-sided 95% CI of the mean.

#### 8.1.3 Number of digits displayed

The number of digits to be displayed in the analysis results will be as follows.

Numeric content	Number of display digits
p value	3 decimal places; however, when it is less than 0.001, it will be described as "<0.001".
Proportion (percentage)	Integer part + 1 decimal place
Rate of change	Integer part + 1 decimal place

Descriptive statistics (minimum and maximum)	Same as the number of digits as original variable
Descriptive statistics (mean, SD, median)	Number of digits of the original variable + 1 digit
Rate of increase in Hb value	Integer part + 4 decimal places
QOL (EQ-5D-5L) index value	Integer part + 3 decimal places

Hepcidin will be measured in units of pg/mL; however, the unit used for tabulation should be ng/mL, and the number of displayed digits should be three decimal places.

## 8.2 Breakdown of subjects

### 8.2.1 Breakdown

For subjects enrolled in the treatment period, the breakdown of each analysis set should be provided. The breakdown of patient cohort will also be provided.

Items: Number of subjects enrolled in treatment period, number and proportion of subjects in the FAS, number and proportion of subjects excluded from the FAS, number and proportion of subjects in the safety analysis set, number and proportion of subjects excluded from the safety analysis set

### 8.2.2 Subjects who discontinued or interrupted their treatment

For subjects enrolled in the treatment period, the number and proportion of subjects who discontinued treatment should be tabulated based on each reason.

Item: Number and proportion of discontinued subjects who enrolled in the treatment period and the number and proportion of reasons for discontinuation.

For subjects enrolled in the treatment period, the number of drug interruptions and the number and proportion of drug interruptions by reasons for drug interruption should be tabulated. The denominator of the proportion should be the sum of the number of interruptions. If there are multiple reasons for a single interruption, they should be counted for each reason and stated as the number of interruption cases.

Item: Number of cases of interruptions of the study drug in subjects who enrolled in the treatment period and the number and proportion of drug interruptions by reasons for study drug interruptions

## 8.3 Demographic and other baseline characteristics

For each analysis set, key demographic and other baseline characteristics are summarized. Frequency and proportion will be provided for discrete variables and descriptive statistics for continuous variables (The 95% CIs of the mean shall not be calculated.). If the safety analysis set is the same as the FAS, the results for the former will not be presented. The data should also be summarized in the FAS by patient cohort.

Table 7.3 Characteristics of demographic and other baseline characteristics

Category	Item	Type of variables
Subject background	Sex (male, female)	Dichotomous
	Age (years) as of informed consent	Continuous
	2 categories: <65, ≥65	Dichotomous
	2 categories: <75, ≥75	Dichotomous
	Duration of nephrogenic anemia (years)	Continuous
	3 categories: <1, 1 to <5, ≥5	Ordinal
	Height (cm)	Continuous
	Body weight (body weight excluding dialysate weight) (kg)	Continuous
	BMI (kg/m  )	Continuous
	2 categories: <25, ≥25	Dichotomous
	3 categories: not Hispanic or Latino, Hispanic or Latino, Unknown	Polytomous
	3 categories: Asian (Japanese), Asian (other), other	Polytomous
	Evaluation data	Hb value (g/dL) on the first day of the treatment period
3 categories: <9, 9 to <11, ≥11		trichotomous
Liver function test (U/L) on the first day of the treatment period		
Category 3: AST and ALT both below the upper limit of normal, either above the upper limit of normal and both ≤2 times the upper limit of normal, either >2 times the upper limit of normal		trichotomous
CRP (mg/dL) on the first day of the treatment period		Continuous
Ferritin (ng/mL) on the first day of the treatment period		Continuous
2 categories: <100, ≥100		Dichotomous
TSAT (%) on the first day of the treatment period		Continuous
2 categories: <20, ≥20		Dichotomous

Smoking status	3 categories: never smoked, ex-smoker, current smoker	Polytomous
Causative diseases of CKD	8 categories: diabetes mellitus, hypertension, autoimmune / glomerulonephritis / vasculitis, interstitial nephritis / pyelonephritis, cystic/hereditary / congenital disease, neoplasm / tumor, unknown, other	Polytomous
Complication	Presence or absence of complications on the first day of the treatment period	Dichotomous
	Presence or absence of hypertension	Dichotomous
	Presence or absence of diabetes mellitus	Dichotomous
	Presence or absence of dyslipidemia	Dichotomous
Iron supplement	With or without iron supplements on the first day of the treatment period	Dichotomous
	2 categories: oral, intravenous	Dichotomous
Iron-containing phosphate binders	With or without iron-containing phosphate binders on the first day of the treatment period	Dichotomous
ESA formulation using for previous treatment (Conversion cohort only)	Types of ESA formulation 4 categories: epoetin (epoetin alfa or epoetin beta), darbepoetin alfa, epoetin beta pegol, other.	Polytomous
	Frequency of administration by type of ESA formulation 7 categories: once a week, twice a week, three times per week, every 2 weeks, every 3 weeks, every 4 weeks, other	Polytomous
	Weekly dose (IU) of epoetin (epoetin alfa or epoetin beta) Weekly dose of darbepoetin alfa ( $\mu\text{g}$ ) Weekly dose of epoetin beta pegol ( $\mu\text{g}$ )	Continuous
Peritoneal dialysis	Duration of peritoneal dialysis (years)	Continuous
	Use or non-use of cyclers	Dichotomous

